16.4 REPEATED OR UNSCHEDULED ASSESSMENTS OF SAFETY PARAMETERS

If a patient has repeated assessments before the date of first dose of double-blind investigational product, the results from the final nonmissing assessment made before the date of the first dose of double-blind investigational product will be used as baseline. If end-of-double-blind-treatment period assessments are repeated or if unscheduled visits occur, the last nonmissing postbaseline assessment during the double-blind treatment period will be used as the end-of-double-blind-treatment-period assessment for generating summary statistics. Likewise, if end of double-blind down-taper period assessments are repeated or if unscheduled visits occur, the last non-missing assessment during the double-blind down-taper period will be used as the end-of-double-blind-down-taper-period assessment for generating summary statistics. However, all postbaseline assessments will be used to determine PCS values for laboratory parameters, vital signs and ECG parameters, and to determine most severe suicidal ideation and most severe suicidal behavior from C-SSRS. All assessments will be presented in the data listings.

16.5 MISSING DATE OF THE LAST DOSE OF INVESTIGATIONAL PRODUCT

When the date of the last dose of investigational product in the study taken during the double-blind treatment period is missing for a patient in the Safety Population, all efforts should be made to obtain the date from the Investigator. If it is still missing after all efforts, then the last available dosing record date will be used as the last dose date.

16.6 MISSING SEVERITY ASSESSMENT FOR ADVERSE EVENTS

If severity is missing for an AE that started before the date of the first dose of double-blind investigational product, an intensity of mild will be assigned. If severity is missing for an AE that started on or after the date of the first dose of double-blind investigational product, an intensity of severe will be assigned. The imputed values for severity assessment will be used for the incidence summary; the values will be shown as missing in the data listings.

16.7 MISSING CAUSAL RELATIONSHIP TO INVESTIGATIONAL PRODUCT FOR ADVERSE EVENTS

If the causal relationship to the investigational product is missing for an AE that started on or after the date of the first dose of double-blind investigational product, a causality of yes will be assigned. The imputed values for causal relationship to double-blind treatment will be used for the incidence summary; the values will be shown as missing in the data listings.

16.8 MISSING DATE INFORMATION FOR ADVERSE EVENTS

The following imputation rules only apply to cases in which the start date for AEs is incomplete (i.e., partly missing).

[REDACTED]

[REDACTED]

[REDACTED]

[REDACTED]

Final

05 Oct 2018

Final

[figure not shown]
05 Oct 2018

The figure consists of seven bar charts arranged in a 7x2 grid. Each chart has 'Grade' on the x-axis (1, 2, 3, 4, 5, 6, 7) and 'Percentage' on the y-axis (0, 100). The charts show the percentage of students in each grade level who are in the 'High' category for different variables. The variables are: 'Number of hours spent on schoolwork per week', 'Number of hours spent on schoolwork per day', 'Number of hours spent on schoolwork per month', 'Number of hours spent on schoolwork per year', 'Number of hours spent on schoolwork per semester', 'Number of hours spent on schoolwork per term', and 'Number of hours spent on schoolwork per quarter'. The 'High' category is consistently the largest across all charts, peaking at approximately 80% for the first three charts and 70% for the last four charts.

| Grade | Number of hours spent on schoolwork per week | Number of hours spent on schoolwork per day | Number of hours spent on schoolwork per month | Number of hours spent on schoolwork per year | Number of hours spent on schoolwork per semester | Number of hours spent on schoolwork per term | Number of hours spent on schoolwork per quarter |
|-------|--|---|---|--|--|--|---|
| 1 | 80 | 75 | 70 | 70 | 70 | 70 | 70 |
| 2 | 80 | 75 | 70 | 70 | 70 | 70 | 70 |
| 3 | 80 | 75 | 70 | 70 | 70 | 70 | 70 |
| 4 | 75 | 70 | 70 | 70 | 70 | 70 | 70 |
| 5 | 75 | 70 | 70 | 70 | 70 | 70 | 70 |
| 6 | 75 | 70 | 70 | 70 | 70 | 70 | 70 |
| 7 | 75 | 70 | 70 | 70 | 70 | 70 | 70 |

16.10 CHARACTER VALUES OF CLINICAL LABORATORY PARAMETERS

If the reported value of a clinical laboratory parameter cannot be used in a statistical summary table because, for example, a character string is reported for a parameter of the numeric type, a coded value must be appropriately determined for use in the statistical analyses. The actual values, as reported in the database will be presented in the data listings.

17.0 CHANGES TO ANALYSES SPECIFIED IN PROTOCOL

No major changes have been made to the original protocol dated 26 Sep 2014.

18.0 **REFERENCES**

Cole TJ. The LMS method for constructing normalized growth standards. *Eur J Clin Nutr.*, 44: 45-60, 1990.

Lu K. Sample size calculations with multiplicity adjustment for longitudinal clinical trials with missing data. *Stat Med* 2012;31:19-28.

19.0

APPENDICES

APPENDIX I PATTERN-MIXTURE MODEL DETAILS

For repeated measures with the monotone missing mechanism, the pattern-mixture model with non-future dependent missing assumption, proposed by Kenward et al. (2003), provides a feasible solution to accommodate certain missing not at random (MNAR) mechanism. The methodology relies on constructing unidentifiable conditional densities using identifiable densities and borrows techniques from standard multiple imputation.

1. Non-Future Dependent Missing Assumption

Assume there are T designed visits in a longitudinal study and let y_i ($i = 1, 2, \dots, T$) represent patient's measurement at Visit i . When the missing mechanism is monotone, the pattern of missing data can be defined by the number of measurements (L) actually observed from the patient. Let $f(y_1, \dots, y_j | L = t)$ denote the conditional density of y_1, \dots, y_j , given that the last observed measurement is at Visit t . Then the overall density function for Pattern t can be written as

$$f(y_1, \dots, y_T | L = t) = f(y_1, \dots, y_t | L = t) f(y_{t+1} | y_1, \dots, y_t, L = t) \times \prod_{s=t+2}^T f(y_s | y_1, \dots, y_{s-1}, L = t) \quad (1)$$

Note on the right hand side of (1) the first factor is clearly identifiable from the observed data, while the second and the beyond are not, due to lack of available data. The second factor $f(y_{t+1} | y_1, \dots, y_t, L = t)$ could be identifiable based on an assumed relationship between $f(y_{t+1} | y_1, \dots, y_t, L = t)$ and $f(y_{t+1} | y_1, \dots, y_t, L \geq t + 1)$. The third and beyond factors $f(y_s | y_1, \dots, y_{s-1}, L = t)$ (with all $s \geq t + 2$) could be identifiable with the help of non-future dependent missing assumption.

For longitudinal data with dropouts, non-future dependent missing (NFD) mechanism (Kenward et al., 2003) assumes that the unidentifiable conditional distributions of y_s ($s \geq t + 2$), given earlier measurements, in Pattern t , is equal to the corresponding distribution in patterns $L \geq s - 1$:

$$f(y_s | y_1, \dots, y_{s-1}, L = t) = f(y_s | y_1, \dots, y_{s-1}, L \geq s - 1) \quad (2)$$

The right hand side of (2) can further be partitioned into

$$f(y_s | y_1, \dots, y_{s-1}, L \geq s-1) = \sum_{j=s-1}^T \omega_{s-1,j} f(y_s | y_1, \dots, y_{s-1}, L = j) \quad (3)$$

Where mixture probabilities $\omega_{s-1,j}$ are:

$$\omega_{s-1,j} = \frac{\alpha_j f(y_1, \dots, y_{s-1} | L = j)}{\sum_{t=s-1}^T \alpha_t f(y_1, \dots, y_{s-1} | L = t)}, \text{ and } \alpha_j \text{ represents the fraction of } \\ \text{patients from Pattern } j. \quad (4)$$

Each factor of the unidentifiable conditional distribution of y_s ($s \geq t+2$) on the right side of (1) can be expressed using the following:

- $f(y_s | y_1, \dots, y_{s-1}, L = s-1)$, the unidentifiable conditional distribution of the first missing in pattern $s-1$,
- $f(y_s | y_1, \dots, y_{s-1}, L = j)$, the identifiable conditional distributions of y_s given y_1, \dots, y_{s-1} of pattern j ($j \geq s$), and
- α_j , the fraction of patients from pattern j ($j \geq s-1$).

So under NFD, all the unidentifiable conditional distribution on the right side of (1) can be estimated and missing value could be therefore imputed based on the assumption for unidentifiable conditional distribution of the first missing.

We re-formulate the partition in (3), for $s \geq t+2$, as the following:

$$f(y_s | y_1, \dots, y_{s-1}, L = t) = \delta_{s-1} f(y_s | y_1, \dots, y_{s-1}, L = s-1) + (1 - \delta_{s-1}) f(y_s | y_1, \dots, y_{s-1}, L \geq s) \quad (5)$$

for $s \geq t+2$ with $\delta_{s-1} = \omega_{s-1,s-1}$.

Therefore, under monotone missing and NFD assumption, the unidentifiable conditional densities for Visit s in Pattern t ($s \geq t + 2$) can be expressed as a mixture distribution of $f(y_s | y_1, \dots, y_{s-1}, L = s - 1)$ - the unidentifiable conditional distribution of the first missing measurement y_s in Pattern $s - 1$, and $f(y_s | y_1, \dots, y_{s-1}, L \geq s)$ - the identifiable conditional distribution of y_s from all the patterns with observed data at Visit s or beyond:

$$f(y_s | y_1, \dots, y_{s-1}, L \geq s) = \sum_{j=s}^T \lambda_{s-1,j} f(y_s | y_1, \dots, y_{s-1}, L = j) \quad (6)$$

where the mixture probability

$$\lambda_{s-1,j} = \omega_{s-1,j} / (1 - \omega_{s-1,s-1}) = \frac{\alpha_j f(y_1, \dots, y_{s-1} | L = j)}{\sum_{t=s}^T \alpha_t f(y_1, \dots, y_{s-1} | L = t)} \text{ for } j \geq s, \text{ where } \alpha_j \text{ is the fraction of} \quad (7)$$

patients from Pattern j .

The conditional densities for the first missing are selected as:

$$f(y_s | y_1, \dots, y_{s-1}, L = s - 1) = f(y_s - \Delta | y_1, \dots, y_{s-1}, L \geq s) \text{ for } s = 2, \dots, T, \quad (8)$$

Note that the two distributions only differ by a shift (Δ) parameter. When $\Delta = 0$, the missing value y_s in Pattern $s - 1$ is imputed based on the distribution of all observed data up to Visit s , as a result, leading to missing at random (MAR) missingness. When $\Delta \neq 0$, (8) will introduce a scenario of MNAR. The similar idea was also presented in the recent publication “The Prevention and Treatment of Missing Data in Clinical Trials” by the National Academies Press. The selection of the plausible values for the shift parameter (Δ) is discussed in Section 3 of this appendix.

Note that per recommendation in Wang and Daniels (2011), only the observed data within pattern is assumed to be multivariate normal. The observed data distribution can be expressed in terms of the marginal distribution of baseline measurement and the conditional distributions of postbaseline measurements given earlier measurements. Assuming that these distributions are normal, the linear regression of each observation on prior observations will yield least-squares estimates of model parameters that can be utilized for independent posterior draws of model parameters for observed data. Multiple imputation approach will be used to estimate the overall mean at the final time point.

2. Imputation Procedure

All the missing data will be imputed to create complete datasets, then statistical analysis can be performed using appropriate techniques such as ANCOVA. The imputation can accommodate MNAR missing data mechanisms, based on the theory discussed in the previous section.

The model parameters for each dropout pattern, i.e., the mean, variance and proportions of observations in each pattern, are drawn from their posterior distributions prior to the imputation of missing data for a single imputation.

The details of imputation within a pattern, say Pattern t , are as the following:

Step 1. Impute the first missing value y_{t+1} for each patient in Pattern t ($t = 1, \dots, T - 1$):

- a. Compute estimates of mixture probabilities $\lambda_{s-1,j}$ in (7) with $s = t+1$ given the posterior draw of proportions of observations in each pattern and the posterior draw of regression parameters for the observed data.
- b. Draw a random integer from $\{s, \dots, T\}$ to index a component distribution on the right hand side of (6), using mixture probabilities obtained in a). Draw y_{t+1}^* from the identified component normal distribution. Impute the missing y_{t+1} as
$$\tilde{y}_{t+1} = y_{t+1}^* + \Delta.$$

Step 2. Impute the rest of the missing values of $y_{t+2}, y_{t+3}, \dots, y_T$ for patients in Pattern t :

Starting with imputation for y_{t+2} , first, similar to Step 1, draw y_{t+2}^* from the normal mixture (6) based on the observed y_1, \dots, y_t and the already imputed \tilde{y}_{t+1} for the patient.

Then the missing y_{t+2} is imputed as $\tilde{y}_{t+2} = y_{t+2}^* + \Delta$ with probability δ_{t+1} and as $\tilde{y}_{t+2} = y_{t+2}^*$ with probability $1 - \delta_{t+1}$, where the mixture probability $\delta_{t+1} = \omega_{t+1,t+1}$ is obtained from (4) given the posterior draw of proportions of observations in each pattern and the posterior draw of regression parameters for the observed data.

Missing values of y_{t+3} through y_T can be imputed similarly as y_{t+2} .

To summarize, the imputations of y_{t+1} through y_T is done recursively within each Pattern t (for all $t = 1, \dots, T - 1$) to create a complete dataset after imputation is done for all patterns with missing values.

The above imputation procedure is applied to all subjects in each missing data pattern to create a single imputed data set. Repeating the process of drawing parameters from the posterior distribution and imputing missing data given the posterior draw m times will yield m imputed data sets. The observed or imputed values at the final data point are averaged to obtain the overall mean estimate for each imputed data set, and the multiple imputation estimate is obtained by averaging the estimates across m imputations.

In this sensitivity analysis, m is set to equal to 20. The value of m is discussed in the context of imputation efficiency in standard multiple imputation theory (Rubin, 1987, p. 114), and $m = 20$ would provide at least 96% of relative efficiency as compared with using a large number of imputations (SAS/STAT User's Guide, p. 3796).

3. Determination of the Shift Parameter Values

The common shift parameter Δ is the difference between the mean of y_{t+1} among those who drop out at Visit t and those who remain beyond Visit t ($1 \leq t \leq T-1$). The exact value of Δ is unknown and can't be estimated from data because of missingness. The magnitude of Δ depends on the medical aspects of the trial. Using relevant historical data, one may select Δ as a proportion of the sample standard deviation or a proportion of observed treatment efficacy.

References:

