9.2 MEASUREMENT OF TREATMENT COMPLIANCE

[REDACTED]

10.0 **EFFICACY ANALYSES**

The efficacy analyses will be based on the ITT Population. *Baseline* for efficacy is defined as the last nonmissing efficacy assessment (at or prior to Visit 2) before the first dose of double-blind investigational product. All statistical tests will be 2-sided hypothesis tests performed at the 5% level of significance for main effects. All confidence intervals will be 2-sided 95% confidence intervals, unless stated otherwise.

For efficacy analyses in which study center is a factor, a small center will be defined as a center with fewer than 2 patients in any treatment group in the ITT Population. Small centers will be pooled to form pseudo-centers so that each treatment group includes at least 2 ITT patients within the center. Pooling will be done (within each country first) using the following algorithm:

Based on the number of ITT patients, small centers will be ordered from the largest to the smallest, and centers of the same size will be ordered from the largest center code to the smallest center code. The pooling process starts with the largest small center from the top, which will be pooled with the smallest from the bottom until a non-small pseudo center is formed. The process will be repeated using the small centers left out after the first pass. If any centers are left out at the end of the process, they will be pooled with the smallest pseudo center. If there is more than 1 smallest pseudo center, the pseudo center with the smallest center code will be selected. In case that the pseudo center formed by pooling all small centers is still a small center, it will be pooled with the smallest non-small center. If there is more than 1 smallest non-small center, the one with the smallest center code will be selected.

These pseudo-centers will be used for all efficacy analyses when the model is adjusted for study center.

By-visit analyses based on the mixed-effects model for repeated measures (MMRM) using the observed case (OC) approach will be performed for all continuous efficacy parameters with multiple post-baseline measurements.

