The pattern for the pattern-mixture model will be defined by the patient's last visit with an observed value. The observed CDRS-R total score at a visit is assumed to have a linear relationship with the patient's prior measurements. The missing values will be imputed under the assumption that the distribution of the missing observations differs from that of the observed only by a shift parameter value Δ . The dataset with missing values imputed will be analyzed using an ANCOVA model with treatment group and pooled study center as factors and baseline CDRS-R total score as a covariate for between-treatment group comparisons at Week 8. The imputation of missing values and the analysis will be performed multiple times and the inference of this sensitivity analysis will be based on the combined estimates using the standard multiple imputation technique. The range of values for the shift parameter Δ is selected as 0 to 6 based on experience with historical data.

More details of the proposed pattern-mixture model approach (e.g., the models for the pattern-specific identifiable densities and the unidentified conditional distributions, the shift parameter Δ , and the multiple imputation algorithm) are provided in Appendix I to this SAP.

To examine the consistency of the primary efficacy results across study centers, the treatment differences versus placebo treatment groups (mean \pm SE) in the change from baseline to Week 8 in CDRS-R total score will be graphed by pooled study center.

The comparison of fluoxetine vs. placebo will be performed to assess study assay sensitivity.

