14.0 DETERMINATION OF SAMPLE SIZE

The primary efficacy parameter is the change from baseline to Week 8 during the double-blind treatment period in CDRS-R total score. A sample size of 400 patients (160 per group for placebo and vilazodone, and 80 for fluoxetine) was initially planned to provide 85% power to detect an effect size of 0.36 (treatment group difference of 4 units relative to pooled standard deviation of 11.1) for the primary efficacy parameter, based on an MMRM model using simulation method (Lu, 2012). The simulation assumed a correlation of 0.7 between the repeated measures, and a dropout rate of 17%, based on historical studies in pediatric patients with MDD.

Based on the planned blinded interim analysis which included the first 300 randomized patients (75% of the initial sample size), the study sample size was increased to a total of 455 patients (182 per group for placebo and vilazodone, and 91 fluoxetine patients) based on a pooled standard deviation of 12.3. During the teleconference with the FDA on the increased sample size, the FDA recommended a second interim analysis to be performed when the study enrolled the initially planned sample size of 400 patients. The second interim analysis included 427 randomized patients and the pooled standard deviation was 12.43. Therefore, a sample size of 470 patients (188 per group for placebo and vilazodone, and 94 for fluoxetine) is required to maintain the 85% statistical power to detect a treatment difference of 4 units for the primary efficacy endpoint.

[figure not shown]

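### With only 20 imputations, the pattern-mixture sensitivity analysis carries avoidable seed noise: under the SAP's planning assumptions, a many-imputation p-value of 0.045 comes out above 0.05 in about 27% of runs

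*SAP*

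**What the plan says.** SAP Section 10.1 names two sensitivity analyses for the primary endpoint, LOCF and a pattern-mixture model. The second imputes missing CDRS-R totals with a shift Δ from 0 to 6, analyses Week 8 by ANCOVA, and pools: "the inference of this sensitivity analysis will be based on the combined estimates using the standard multiple imputation technique". Section 10.0 sets the test level: "All statistical tests will be 2-sided hypothesis tests performed at the 5% level of significance for main effects".

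The number of imputations is fixed in Appendix I, part 2: "In this sensitivity analysis, m is set to equal to 20". The reason given is that this number "would provide at least 96% of relative efficiency as compared with using a large number of imputations". Appendix I gives no Monte Carlo error criterion. It names no seed either, but the software section (15.0) is partly redacted and output specifications are in a separate document, so nothing here rests on a missing seed.

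**The concern.** Relative efficiency compares the variance of the pooled estimate at m imputations with its variance at infinitely many. It can be close to 1 while the p-value still differs visibly between two runs on the same data. This analysis is meant to show whether the primary result survives departures from missing at random. The natural reading is therefore whether significance holds as Δ rises, and how fast the difference erodes. If the p-value lies near 0.05 at some Δ, the answer can depend on the seed, in either direction. If the Δ runs are seeded independently, part of the apparent erosion from one Δ to the next is noise rather than the effect of the assumption.

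What is at stake is the credibility of the robustness statement. The confirmatory conclusion is not affected.

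**Working it through.** **Inputs.** All four come from SAP Section 14.0:

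- Patients per arm: "a sample size of 470 patients (188 per group for placebo and vilazodone, and 94 for fluoxetine) is required".
- Within-patient correlation: "The simulation assumed a correlation of 0.7 between the repeated measures".
- Spread of the change score: "The second interim analysis included 427 randomized patients and the pooled standard deviation was 12.43".
- Expected loss of patients: "a dropout rate of 17%, based on historical studies in pediatric patients with MDD".

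The protocol's visit numbering (Baseline is Visit 2, Week 8 is Visit 8) gives six post-baseline visits. Assumptions added here: compound symmetry, and monotone dropout spread evenly over the visits.

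**1. The plan's own figure.** Relative efficiency is 1/(1 + FMI/m), where FMI is the fraction of missing information. At m = 20:

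- FMI 0.10: 1/(1 + 0.10/20) = 0.995
- FMI 0.17: 0.992
- FMI 0.83: 0.960

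The 96% statement is correct for any plausible FMI.

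**2. Missing information.** Summing the information over the dropout patterns gives an effective sample fraction of 0.924 at Week 8, so FMI is about 1 − 0.924 = 0.076. The effective n per arm is 188 × 0.924 = 173.7, and the SE is 12.43 × √(2/173.7) = 1.334. Power for 4 points is Φ(4/1.334 − 1.96) = 85%, which matches the SAP, so these inputs agree with its planning model.

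**3. Noise in the estimate.** The between-imputation variance is B ≈ 0.076 × 1.334²/1.05 = 0.129. The Monte Carlo SD of the treatment difference at m = 20 is √(0.129/20) = 0.080 points. Between two independently seeded Δ runs it is 0.080 × √2 ≈ 0.11.

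**4. Noise in the p-value.** Fix the many-imputation result, then draw the pooled estimate from N(Q, B/m) and the between-imputation variance from B·χ²(m−1)/(m−1). Set the total variance to W + (1 + 1/m)B, where W is the within-imputation variance, and refer the ratio to t with Rubin's degrees of freedom. At FMI 0.076 and m = 20:

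| Many-imputation p | Central 95% of runs | On the other side of 0.05 |
|---|---|---|
| 0.055 | 0.041 to 0.074 | 25% (below) |
| 0.050 | 0.037 to 0.068 | – |
| 0.045 | 0.033 to 0.062 | 27% (above) |
| 0.040 | 0.029 to 0.055 | 9% (above) |
| 0.030 | 0.022 to 0.042 | 0.1% (above) |

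Barnard-Rubin degrees of freedom give the same 27%. Direct simulation of a simplified sequential-regression imputation with 188 per arm gives 26.6% at Δ = 0 and 27.2% at Δ = 6.

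**5. Dependence on FMI and m.** Chance of p > 0.05 when the many-imputation p is 0.045:

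| m | FMI 0.07 | 0.10 | 0.12 | 0.17 |
|---|---|---|---|---|
| 20 | 26% | 31% | 33% | 38% |
| 100 | 6% | 10% | 13% | 19% |
| 200 | 1% | 4% | 5% | 10% |
| 500 | about 0% | 0.2% | 0.5% | 2% |
| 1000 | about 0% | about 0% | about 0% | 0.2% |

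If the baseline score is also correlated 0.7 with later scores, FMI is about 0.13 and the m = 20 figure is 34%. Setting FMI to the full 17% dropout gives the last column.

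**6. Reading across Δ.** Appendix I applies one common shift to both arms, so Δ moves the treatment difference roughly by Δ times the between-arm imbalance in dropout. As an illustration only, assume a 3-percentage-point imbalance. One unit of Δ then moves the difference by about 0.03 points, and the full range by about 6 × 0.03 = 0.18. Against noise of 0.11 between independently seeded runs, a one-unit step would be mostly noise and the full sweep about 0.18/0.11 = 1.6 noise SDs.

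**The case against.** The strongest reply is that 27% applies only to a result that happens to lie just under 0.05. Averaged over possible trials, with one analysis at one Δ, m = 20 and unlimited imputations disagree on significance in a little over 1% of trials at the planned 4-point difference. The figure is about 2% at 2 or 3 points and 0.6% with no effect, split about equally in both directions. That is right, and it is why this is a minor point.

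Nor does any decision depend on the analysis. The primary MMRM uses observed cases without imputation, the fixed sequence is gated only by the primary test, and the SAP sets no pass/fail rule or tipping-point threshold. That also stands. Noise of 0.080 points is about 6% of the SE (0.080/1.334) and 2% of the 4-point target, so a reading by estimates and intervals would barely change.

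The relative-efficiency statement is true, so there is no internal error. It answers a different question from the one this analysis is read for.

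The Δ-to-Δ argument needs independently seeded runs, and the visible text does not say whether the seed is common. With a common seed most of that noise cancels, but the p-value noise at each Δ remains.

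Finally, m = 1000 is one choice among several. At FMI of 0.07 to 0.10, m = 500 already brings the figure to 0.2% or less. None of this is a reason to keep m = 20, because a larger number has no statistical cost.

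**Conclusion.** The concern holds as a minor, freely removable weakness in a sensitivity analysis. With m = 20, a many-imputation p-value of 0.045 is reported above 0.05 in about 27% of runs, given an FMI of about 0.076. The documents do not state that FMI. It follows from their 17% dropout and 0.7 correlation under compound symmetry and evenly spread monotone dropout. Over FMI of 0.07 to 0.17 the range is 26% to 38%, so 27% is near the low end. The noise can also create apparent robustness: a many-imputation p-value of 0.055 falls below 0.05 in about 25% of runs. The effect fades quickly away from the boundary and does not touch the primary or key secondary test.

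**What to change.** In SAP Appendix I, part 2, change the number of imputations from 20 to 1000, or at least 500. Replace the relative-efficiency sentence with a Monte Carlo criterion, for example that m is chosen so that the p-value and the treatment difference at each Δ are stable across seeds. Pre-specify the seed and use the same one for every Δ; if a seed is already set in text not visible here, confirm that it is common to all Δ values. Report the Monte Carlo standard error with each pooled result.

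The cost is computer time and a short edit to one appendix. The estimand, imputation model, Δ range and data collection are unchanged.
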